Due to the problem of attrition in the control group, it has been suggested in the last International Myopia Conference that controlled field studies be performed by a virtual group, without performing a non-inferiority study, since atropine 0.01% could not be taken as gold standard because it is not yet approved and as we said, it is off-label in Argentina. Data on progression in Asia or Europe could be used for this virtual control group, but it would be more convenient to have a virtual control group in one's own living environment. In the case of our country there is already a possible control group of 114 children of 12 years of age on average who were followed up with cycloplegia during the years pre-pandemic and from which it is known that the progression was from 0.43+/-0.52 diopters in one year.³⁶

It is thus proposed to perform a prospective clinical study in 100 children who will be enrolled when in the usual consultation for their eyeglasses control they can choose to do the treatment accessible in our environment (the diluted atropine drop) or a treatment that is possibly equally effective with special glasses designed in our environment. It is

expected that there will be similarity of effect on progression because the lens is based on the principles of defocusing of eyeglasses and contact lenses already proven by the international industry.³⁷ Our lens has the characteristic of being much simpler in its carving and construction, making it more economical for our environment where it has already been presented from the theoretical point of view.³⁸

Moreover, the special myopia control spectacle lacks the possible toxic effects of a drop instilled in the eye for many years until emerging adulthood. In addition, to avoid including children who may have rapid progressions to high myopia, treatment will be offered only to children over 8 years of age. In our environment, where children are outdoors a lot, the progression is slower than in Asian countries and is around -0.50 diopters per year, as we said.³⁶ A strong myopia is the one that exceeds -5.00 diopters.³⁹ Thus the risk for a child included in this project is to progress -0.25 diopters in six months (the resolution limit of the measurement method), so each child who does not respond well with arrest of progression at six months may be removed from the protocol and switched to atropine treatment.

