ophthalmology offices that are members of the research team. The opticians and ophthalmologists will be asked to watch a video on myopia control developed by the principal investigators where this treatment methodology is explained during the evaluation process at the center of care. The opticians will verify the optical centration in the frames chosen ad hoc, with a modern digital centration system provided by the sponsors. After 15 days, when the glasses with the correct centering are ready, the subjects will go to the optician's office to try on the glasses in that room. On this occasion, as always in these cases, the optician will evaluate the subject's adaptation and mobility in the optician's shop, instructing the child to wear the glasses at home for a couple of days and then to wear them for as long as possible.

SAMPLE AND SAMPLE SIZE

The sample size will be 50 subjects of both genders to compare with the studies abroad that consist of an n between 40 and 90 subjects and the natural history in our country that counted 114 subjects. There will be a group of subjects who will be treated with the nationally designed defocus glasses. Statistical calculation for a difference of 0.25 diopters in progression with respect to controls, for a standard deviation of 0.50 diopters gives an $n = 31$ subjects and taking into account a 20% loss to follow-up the n should equal 38 subjects in the group. Thus reaching 50 subjects exceeds expectations.

METHODS

This field study to test tolerance and percentage of effectiveness of defocus lenses in the control of myopia will include boys and girls from 8 to 15 years of age who voluntarily

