One month after the delivery of the spectacle, the principal investigator in charge will make a telephone call to the parent of the study subject conducting the tolerance survey and thus verifying adherence to spectacle use. The survey is detailed in the attached medical record and responses will be uploaded into the computerised web-based system that will be developed for this study. The system will automate the alerts for these safety calls with automatic emails sent to the principal investigator in the month of spectacle delivery.

PLAN FOR ANALYSING THE RESULTS

The results of numerical variables shall be expressed as mean and standard deviation or median and interquartile range according to whether they are normally or skewed. Nominal variables will be expressed as absolute frequency and percentage. For the comparison of numerical variables, Student's t-test or Mann Whitney U-test will be used as appropriate. Nominal variables will be compared using the Chi-square test or Fisher's exact test as appropriate. A p-value of $p \leq 0,05$.

HUMAN RESOURCES

[name] and [name] are in charge of the design and control of the research. Statistical analysis will be performed by [name]. Physicians accredited to treat patients will have to demonstrate the ability to perform routine consultations for myopia control, refraction studies under cycloplegia and optical biometry. Once accredited, they will have a username and password to upload their data into the web form. Accredited doctors will be in permanent communication with doctors [name] and [name]. There will be a myopia progression monitoring system within the computerised system that will send reports if any child progresses more than 0.25 dioptres in six months to alert researchers so that precautionary measures can be taken in such cases.

MATERIAL RESOURCES

Optotypes, Retinoscope, Autorefractometer and Biometer posters of accredited institutions.

Approximately four institutions with a high turnover of paediatric consultations are expected to be accredited for an estimated enrolment time of 6 months.

Peripheral defocus spectacles will be provided by the sponsor (NOVAR) free of charge to all study subjects for one calendar year with the possibility of extending the study for two years. At the end of the study, if the expected positive results are found, the glasses will remain in the possession of the study subjects.

FINANCIAL RESOURCES

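### The only parametric test named, Student's t, pools the SDs of about 40 lens children and 114 earlier controls; Welch's t would avoid a possible loss of power at almost no cost

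*Combined protocol and SAP*

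**What the plan says.** The section PLAN FOR ANALYSING THE RESULTS gives one rule for every numerical variable: "For the comparison of numerical variables, Student's t-test or Mann Whitney U-test will be used as appropriate". The only distinction drawn nearby concerns summary statistics, which are to be "mean and standard deviation or median and interquartile range according to whether they are normally or skewed". Unequal variances are not mentioned, and no confidence interval is planned. The significance threshold is 0.05, with no statement of one or two sides.

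SAMPLE AND SAMPLE SIZE plans 50 lens children, allows 20% loss, and compares them with "the natural history in our country that counted 114 subjects". Its calculation is for a "difference of 0.25 diopters in progression with respect to controls, for a standard deviation of 0.50 diopters". CURRENT STATE OF RESEARCH reports for those controls that "the progression was from 0.43+/-0.52 diopters in one year", and METHODS says they were followed in 2018-2019 by a different study group. CURRENT STATE OF RESEARCH also speaks of 100 children, which conflicts with the 50.

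INCLUSION / EXCLUSION CRITERIA takes out of the protocol, during follow-up, lens children who at six months do no better than expected without treatment. The controls have no matching rule. Progression is the secondary objective (OBJECTIVES).

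**The concern.** Student's t is exact when both groups share one SD. With equal group sizes it tolerates a departure well; with 40 against 114 it does not, because the pooled SD is mostly that of the larger group. If the smaller group is less variable, the standard error comes out too large, the test is conservative and power is lost. If the smaller group is more variable, the standard error is too small and false positives exceed 5%.

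Two features of this plan make a narrower lens group foreseeable. The six-month removal trims the fast-progressing tail of that group alone. And the study aims at a "percentage of effectiveness"-type effect: METHODS opens with "This field study to test tolerance and percentage of effectiveness of defocus lenses". If each child's progression falls by a proportion, the spread falls with the mean. The likelier cost is therefore wasted power in a comparison whose power at equal SDs is only about 74%.

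**Working it through.** **The plan's own figure.** With two-sided 5% and 80% power (neither is stated), the one-sample form gives ((1.960 + 0.842) × 0.50 / 0.25)² = 31.4, matching the stated 31. Then 31 × 1.20 = 37.2, rounded up to 38. One SD is used throughout, so the calculation says nothing about unequal spread.

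**Inputs for the check.** Lens n = 50 × 0.80 = 40. Control n = 114, SD 0.52 D. Difference 0.25 D for power. Two-sided 5% and normal data are assumed. The lens SD is an assumption, except for 0.50 D, the planning value.

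**Formulas.**
- Pooled SE = √{[(39 s₁² + 113 × 0.52²) / 152] × (1/40 + 1/114)}
- True SE, which Welch estimates = √(s₁²/40 + 0.52²/114)

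At s₁ = 0.35:
- Pooled: √{[(4.778 + 30.555) / 152] × 0.03377} = 0.0886
- True: √(0.003063 + 0.002372) = 0.0737, so the pooled SE is 20% too large.

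At s₁ = 0.50:
- Pooled: √{[(9.750 + 30.555) / 152] × 0.03377} = 0.0946
- True: √(0.006250 + 0.002372) = 0.0929, so the pooled SE is 2% too large.

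**Error rates and power by simulation, 40 v 114.**

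| Lens SD (D) | Pooled SE | True SE | Student false-positive rate | Power, Student | Power, Welch |
|---|---|---|---|---|---|
| 0.35 (assumed) | 0.0886 | 0.0737 | 1.9% | 84.5% | 92.0% |
| 0.40 (assumed) | 0.0904 | 0.0798 | 2.7% | 81% | 87% |
| 0.45 (assumed) | 0.0924 | 0.0862 | 3.6% | 78.2% | 81.7% |
| 0.50 (planning SD) | 0.0946 | 0.0929 | 4.6% | 75.0% | 75.6% |
| 0.52 (equal SDs) | 0.0956 | 0.0956 | 5.0% | 73.9% | 73.3% |
| 0.65 (assumed) | 0.1022 | 0.1137 | 7.8% | not comparable | 58% |

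Welch stays at 5.0% in every row. In the last row Student's power is not comparable because its error rate is not 5%.

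**Is a lens SD of 0.35 to 0.45 D plausible?** An illustration of the removal rule alone: take a one-year SD of 0.52 D, mean progression 0.43 − 0.25 = 0.18 D, half-years correlated 0 to 0.5, and removal of children progressing more than 0.25 D in six months. The half-year mean is 0.09 D.
- Correlation 0: half-year SD = 0.52/√2 = 0.368. The cut is at (0.25 − 0.09)/0.368 = 0.435 SD, so 67% remain. The variance of the first half-year falls to 0.469 of its value, and the one-year SD is 0.368 × √(0.469 + 1) = 0.45 D.
- Correlation 0.5: half-year SD = 0.52/√3 = 0.300. The cut is at 0.533 SD, so 70% remain. The variance factor is 0.495, and the one-year SD is 0.300 × √(2.25 × 0.495 + 0.75) = 0.41 D.

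The rule alone could thus bring the SD to about 0.41 to 0.45 D. Reaching 0.35 D would need some narrowing by the lens as well.

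**If 100 are enrolled.** With 100 × 0.80 = 80 completers, Student's false-positive rate is 3.7% at lens SD 0.35 and about 6% at 0.65. At 0.35 the power is 97.0% v 97.8%. With all 100 followed, the rate is 4.5% to 5.7% for lens SDs from 0.35 to 0.78.

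**Mann-Whitney** at 40 v 114 also drifts: 2.9% at 0.35 and 6.0% at 0.65. It does not estimate the 0.25 D mean difference, and it needs the individual control values.

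**The case against.** The strongest reply is that the documents do not show an actual error. The only two SDs they give are 0.50 and 0.52 D, and there the two tests are practically the same. That stands, with one limit: 0.50 is a single planning value, not an observed lens-group SD, so it does not show that the spreads will be equal.

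A reader might infer that the plan's false-positive rate is wrong, or inflated. The documents do not support this. Inflation needs a more variable lens group. Greater multi-site measurement noise is only a conjecture: the documents do not say how many sites or examiners produced the control data, and CENTERS OF ATTENTION plans training towards a joint protocol. Nor should the low rates at 0.35 to 0.45 D be read as the test's behaviour under no effect. A proportional effect narrows nothing when the effect is zero. Removal of non-responders would still narrow the spread, but it would also shift the mean, which is a matter of bias and not of variance.

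Proportional scaling is itself uncertain. A percentage can describe the group summary only, the control SD (0.52) exceeds the mean (0.43), and measurement noise would not shrink with treatment.

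A reader might also say that the planned interval is wrong. None is planned, so the point applies only if one is reported. Lastly, leaving the test to what is appropriate gives the analyst some room. But the only criterion in the section is shape of distribution, which does not lead to Welch.

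**Conclusion.** The point holds as a cheap improvement to the choice of test. Student's t is the only parametric option, the groups are unequal and not randomised, and the plan itself has a rule that could narrow one group's spread.

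The size depends on an unknown lens SD. It is negligible at 0.50 v 0.52 D and small if 100 children are enrolled. At an assumed lens SD of 0.45 to 0.35 D, with 40 v 114, it is a loss of about 3 to 7 points of power for 0.25 D. The opposite case, 7.8% false positives at 0.65 D, is a bound under an unsupported assumption and not an expectation.

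These figures rest on normal data, a two-sided 5% test, 20% loss from 50, and a control SD of 0.52 D. The primary objective, tolerance and adherence, is untouched.

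**What to change.** In PLAN FOR ANALYSING THE RESULTS, name the Welch unequal-variance t-test in place of Student's t for progression in the lens group v the virtual control, with its own confidence interval if one is reported. Do not let a preliminary variance test decide between the two.

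Welch needs only means, SDs and group sizes, so it can be computed from 0.43 ± 0.52 D, n = 114, even without individual control data. METHODS gives the control mean as 0.45 D, so the value to be used should be settled at the same time.

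The cost is one line of text and, if the SDs are equal, under 1 point of power (73.9% v 73.3%). The change does not remove bias from non-concurrent controls or from removing non-responders; those need separate treatment.

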In the report of the countries that make up the Ibero-American Epidemiological Network for Eye and Eye Health, for the period 2009-2010, the lowest prevalence for children was reported in Argentina (1.2%) and the highest in Ecuador with 25.2%. The low values in Argentina were determined only in rural areas and this is why they are so contrasting with the rest of the countries in the network. Another study from Argentina conducted in office workers in the city of Buenos Aires has found a prevalence of myopia of approximately an 25%.¹² In Colombia, the diagnosis of myopia in the 2009-2010 period was 21% and 22%, respectively, with a higher prevalence in the 5 to 14 years age group, followed by the 15 to 44 years age group.¹³

Myopia progression can trigger pathologic changes in the eyeball that affect structures such as the lens, retina, choroid and macula. Myopia progression doubles the risk of nuclear cataract,¹⁴ open-angle glaucoma,¹⁵ maculopathy, choroidal neovascularization and retinal detachment.¹⁶ These degenerative changes are the most frequent cause of vision loss with irreversible blindness.¹⁷ and are associated with refractive values of more than 5-6 diopters of myopia in adult life.^{6,18-21}

Research work on preventive treatments, to date, is generally conducted on children 6-12 years of age,^{22,23} and a few unpublished studies of natural history or treatment effectiveness in

adolescents are ongoing. In addition, children who begin with their myopia between the ages of 5 and 7 years of age when they do not yet read intensely, they often have genetic myopia that may develop high myopia.²⁴ In turn, these children are the ones most at risk for adult disability due to myopic maculopathy.¹⁷ It has been suggested that these children should be treated according to the myopia consensus of the SAOI Myopia Study Group with atropine 0.01% or 0.05% to prevent such rapid progression.²⁵ Children over 8 years of age progress at a slower rate, even more slowly as they get older.²⁶

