Given the above-mentioned background, the following study has been designed to evaluate the arrest of myopia progression with the daily use of nationally designed glasses, comparing such progression with a virtual control group of similar age in a population of myopic children and adolescents of the same environment in our country.

WORKING HYPOTHESIS

The nationally designed lenses can be as effective as the proven international industry designs that have been subjected to controlled trials against natural history of the disease.

PURPOSE

To treat a group of consecutive volunteer patients who choose between the affordable treatment in our environment (daily diluted atropine drops for several years) or the special lenses for myopia control designed by the National Industry. The purpose is to compare the progression during one year with the national lenses with respect to the progression with the foreign lenses and/or with the natural history of a virtual control group.

OBJECTIVES

Primary

To assess whether the intervention with locally designed spectacles is well tolerated and adhered to with daily use in childhood and adolescence.

Secondarily

To assess whether intervention with locally designed glasses can control myopia progression in childhood and adolescence.

DEFOCUS GLASSES OF NATIONAL DESIGN

The design of the national defocus lens is based on the original design presented by Carly Lam,⁴⁰ with a 9 mm central zone for distance correction and a correction ring with a +3.50 dioptre defocus between 9 and 32 mm in diameter to act in principle on the para foveal zone which is the one that detects the defocus that governs the growth of the eye.⁴¹ Instead of peripheral defocusing micro lenses that do not alter the visual field in the area of the 32

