mm diameter ring with the treatment,⁴⁰ the national design that was presented has a uniform +3.50 diopter power zone that alters the visual field by 5% at 10 degrees from the circular shaped fovea,³⁸ as presented at the International Myopia Conference a month ago. As it is known that positive defocus in 30-40 minutes of exposure modifies the axial length (measured with Lenstar) by 10 microns due to changes in the choroidal thickness,⁴² The national design has been tested on 17 volunteer subjects showing a significant change of 11 microns in the axial length of their eyes, suggesting this pilot study (in the process of being published) that the lenses should be effective in halting the progression of myopia, as changes in the choroid are the first event in the retinal message that governs ocular growth.⁴³ This, coupled with the survey that gave a good reading tolerance in 70% of the 17 respondents within a month of wearing them, was presented at the Conference and is in the public domain. Respondents found it difficult to walk around with these lenses because they are like an executive bifocal, but tolerated them well for reading at home, with small lateral movements of the head when reading A4 texts or the computer. It is therefore our intention to do a free field test with such lenses on a larger sample.

POPULATION

Consecutive patients between 8 and 16 years of age who attend the institutions accredited for this study. These institutions will be accredited only if they can perform routine studies for myopia control (refraction exam and optical biometry).

USE OF GLASSES

Once the eyeglass prescription has been written by the ophthalmologist, the enrolled patients will be seen in opticians accredited for this study in close proximity to the

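### The natural-history comparison is planned with unadjusted tests, so any age difference from the non-randomised 2018-2019 cohort would bias the estimated lens effect, in either direction

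*Combined protocol and SAP*

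**What the plan says.** All places are in the combined protocol and SAP.

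- **Objective.** Efficacy is the secondary objective: "To assess whether intervention with locally designed glasses can control myopia progression" (Objectives). The primary objective is tolerance and adherence.
- **Comparison.** The Purpose section compares one-year progression "with respect to the progression with the foreign lenses and/or with the natural history of a virtual control group". This point concerns the natural-history comparison only.
- **Comparator.** Current State of Research describes "a possible control group of 114 children of 12 years of age on average", of whom "it is known that the progression was from 0.43+/-0.52 diopters in one year". Methods dates this cohort to 2018-2019 and gives its progression as -0.45 D.
- **Age as a prognostic factor.** The Problem Statement says: "Children over 8 years of age progress at a slower rate, even more slowly as they get older".
- **Comparability.** The study aim, just before the Working Hypothesis, speaks of "comparing such progression with a virtual control group of similar age". Methods expects the treated children to be equivalent to the cohort. Neither section gives a procedure.
- **Treated group.** Population specifies "Consecutive patients between 8 and 16 years of age", and Criteria for Inclusion gives the same range. Methods gives 8 to 15. Under Inclusion / Exclusion Criteria, children enter by opting for the lens.
- **Analysis.** Plan for Analysing the Results gives a Student's "t-test or Mann Whitney U-test will be used as appropriate" for numerical variables and chi-square or Fisher tests for nominal ones, with a p-value threshold of 0.05. It does not name the efficacy outcome or the cohort. No section plans regression, matching, weighting or stratification.

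**The concern.** Without randomisation, nothing in the design makes the two groups alike in age. The protocol treats age as related to progression, yet a two-sample test attributes the whole difference in mean progression to the lens, including any part due to age. The direction follows from the protocol's own statement: an older treated group would progress more slowly even with an inert lens, and a younger group would progress faster even with an effective one.

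At stake is the comparison that would support a claim of control over natural history. It is also the contrast on which the sample size rests (0.25 D with respect to controls).

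**Working it through.** **1. The plan's own figure.** Sample and Sample Size gives n = 31 for a 0.25 D difference with SD 0.50 D. Power and sidedness are not stated; I assume 80% and two-sided 5%. The one-sample formula gives n = [0.50 × (1.96 + 0.84) / 0.25]² = 31.4, which agrees with 31. This form treats the control mean as known and fixed, with no sampling error and no age adjustment. It is not the only route: a one-sided comparison with 114 controls gives 31.6.

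**2. Standard error of the planned contrast.** Inputs: 50 treated children (Sample and Sample Size; Current State of Research mentions 100), 114 controls, SD 0.50 D for treated and 0.52 D for controls.

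SE = √(0.50²/50 + 0.52²/114) = √(0.00500 + 0.00237) = 0.0859 D.

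**3. Bias from an age gap.** Shift b = age gap × slope. The documents give no slope, so 0.03-0.08 D per year of age is an assumption. They do not give the treated group's mean age either. Range midpoints are only stand-ins: 12 for ages 8-16 (no gap) and 11.5 for ages 8-15 (half a year younger). No section suggests a 1-year gap; it is included as a stress case.

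- Two-sided false-positive rate = P(Z > 1.96 − b/SE) + P(Z < −1.96 − b/SE)
- Power for a true 0.25 D, treated younger = P(Z > 1.96 − (0.25 − b)/SE)

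| Age gap | Shift b (share of 0.25 D) | Two-sided false-positive rate | Power if treated younger |
|---|---|---|---|
| 0 | 0 | 5.0% | 82.9% |
| 0.5 year | 0.015-0.04 D (6-16%) | 5.4-7.5% | 78.1-68.6% |
| 1 year | 0.03-0.08 D (12-32%) | 6.4-15.4% | 72.7-50.8% |

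The two-sided rate is the same whichever group is older, but the excess favours the lens only if treated children are older. If they are half a year younger, the chance of a false result favouring the lens falls from 2.5% to 1.6-0.8%.

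**4. After the planned 20% loss.** With 40 completers, SE = √(0.50²/40 + 0.52²/114) = 0.0929 D.

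| Age gap | Two-sided false-positive rate | Power if treated younger |
|---|---|---|
| 0 | 5.0% | 76.8% |
| 0.5 year | 5.3-7.2% | 71.6-61.9% |
| 1 year | 6.2-13.8% | 65.9-44.9% |

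**5. Sensitivity to the slope.** With a steeper assumed slope of 0.05-0.15 D per year, 40 completers and SD 0.50 D in both groups (SE 0.092 D), a 1-year gap shifts the difference by 0.05-0.15 D (20-60% of target). The chance of a false result favouring the lens is then 8-37% if treated children are older. Power is 59-19% if they are younger.

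**6. Precision cost of adjusting for age.** The treated share is p = 50/164 = 0.305, so p(1−p) = 0.212. The squared correlation of group with age is r² = 0.212 × gap² / (0.212 × gap² + SD²), and the SE is multiplied by √[1/(1−r²)]. The within-group age SD is assumed to be 1.5-2 years.

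- 1-year gap, SD 2: r² = 0.212/4.212 = 0.050, SE × 1.026
- 1-year gap, SD 1.5: r² = 0.086, SE × 1.046
- 0.5-year gap: SE × 1.007-1.012
- No gap: no cost

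These are upper bounds, because they ignore the residual variance that age explains.

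**The case against.** The strongest reply is that no section shows an age gap. The cohort averages 12, and so does the midpoint of 8-16. The only other stand-in, 11.5, works against the lens. Nothing points to an older treated group, which is the case that would flatter it. The slope is assumed throughout, and the half-year shift is less than half of one standard error. All of this is correct. It limits the weight the figures can bear, and they are illustrative only. It does not supply a safeguard: midpoints are not means, and the treated mean age depends on who volunteers.

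A second reply is that the protocol already wants controls of similar age and an equivalent group. That is an aim without an age window, matching rule or check behind it. The plan's descriptive summaries could reveal an age imbalance but would not correct it.

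A third reply is that age may not be the main threat. Taking out children who do not respond at six months selects on the outcome, in the lens's favour. Self-selection and calendar period also remain. This stands: adjusting for age cures none of these, and the report should not suggest that it does.

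Finally, the control cohort may exist only as a published summary. The documents do not settle this, so the remedy needs a fallback. Efficacy is also only the secondary objective; the primary one is unaffected.

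**Conclusion.** The concern holds. The only comparative tests given for numerical variables are unadjusted, the natural-history control is external and non-randomised, and the protocol itself says that progression varies with age. The mechanism and direction of bias follow from the documents; whether a gap will occur, and how large it will be, does not.

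Under the assumed 0.03-0.08 D per year of age, half a year's gap is a modest distortion and a full year's gap a material one (12-32% of the 0.25 D target). At equal mean ages there is none. This is a recommended change to the secondary efficacy analysis, made with medium confidence; it is not a fatal flaw.

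**What to change.** **Main analysis.** Specify the natural-history comparison as a linear regression of one-year change in cycloplegic spherical equivalent on group, adjusted for age, using the individual records of the 114 controls once their availability is confirmed. Baseline spherical equivalent is a reasonable second covariate, but that is an assumption: no section says it predicts progression. State in advance how the two eyes of each child are combined. Report the adjusted difference with its 95% CI, give the t-test as unadjusted support, and tabulate age in both groups.

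**Fallback.** If individual records cannot be obtained, use one verified control mean and SD, reconciling 0.43 D (Current State of Research) with 0.45 D (Methods). Include the sampling error of that mean, and state plainly that age confounding is not controlled.

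**Cost.** Analysis-plan wording and a data request. Date of birth and refraction are already on the trial's data form, so nothing more is needed from treated children. Controls with missing covariates may be lost. The precision cost is at most about 3-5% on the SE at a 1-year gap and nil at equal ages.

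**Limits.** Adjustment does not address self-selection, calendar period, the removal of six-month non-responders or the comparison with foreign lenses. The report should say so.
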